## **15.6.** Analysis Populations

Safety Population: Safety outcomes will be assessed for all subjects who are given at least one dose of investigational product.

Full Analysis Set (FAS) Population: Efficacy outcomes will be evaluated using the FAS, defined as all subjects randomized, treated with at least 1 dose of investigational product, and with at least one post-baseline assessment of efficacy.

Per Protocol Population: The per protocol population will be a subset of FAS and include subjects who received at least 80% of study drug and have no major protocol deviations that would impact efficacy assessment.

## 15.7. Alpha Level Considerations

All inferential testing will be performed using two-sided 5% Type I error ( $\alpha$ ), and therefore 2-sided p-values  $\leq 0.05$  will be considered statistically significant in this study.

The first hypothesis test will be the key secondary efficacy endpoint of change in bilateral UEMS from baseline to Study Day 169 using the MMRM model as detailed below. Additional secondary efficacy endpoints tested will be the change in GRASSP prehension performance from baseline to Study Day 169 and of change in SCIM self-care from baseline to Study Day 169.

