8.1 General Principles

- All data processing, summarization and analyses will be performed using SAS Environment / Version 9.4 (or later) of the SAS[®] statistical software package.
- The following principles will be applied to all TFLs unless otherwise stated:

Table 6 Statistical Analysis General Principles

Principle	Value
Significant tests	Two sided and use a 5% significance level
Treatment group labels and order	Part 1: AXER-204 xx mg
presented	Part 2: AXER-204 200 mg; Placebo
Tables	Data in summary tables presented by dose
	cohort/treatment group, assessment (where
	applicable), and visit (where applicable).

Principle	Value
Listings	All data collected presented by dose
	conort/treatment group, subject, and visit (where applicable) unless otherwise specified
Descriptive summary statistics for	Number of subjects (N), mean, standard deviation
continuous variables	(SD), median, minimum, maximum.
Descriptive summary statistics for categorical variables	Frequency counts and percentages [n (%)]
Denominator for percentages	Number of subjects in the analysis population, unless otherwise specified.
Include "Missing" as category	Yes, when the number missing is greater than zero for at least one dose cohort/treatment group.
Display for percentage	One decimal place, except for 100%
Display for 0 percentages	0
Display to one more decimal place than collected value	Mean, Median, Mean Difference
Display to two more decimal places than collected value	Standard Deviation
Limit of precision for displays	3 decimal places
Date Format	DDMMMYYYY
TFL orientation	Landscape
TFL output	For all tables and listings, 2.54 cm for the
	top/bottom/left/right margins and 8-point Courier New font

• For both safety and efficacy analysis, the baseline value will be defined as the last non-missing value before the first dose of study treatment.

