8.5.2.1.3 Subgroup Analysis

Subgroup analyses using the same methods as the primary and secondary analyses as described in sections 8.5.2.1 and 8.5.2.1.1 will be conducted comparing the primary efficacy endpoint between the treatment group and control group to assess consistency of treatment effects across potential prognostic factors.

The following subgroup of mITT will be analyzed for the primary efficacy endpoint.

- AIS grade (A, B vs C, D)
- Received study drug in Part 1 vs. Did not receive study drug in Part 1
- AIS grade (A vs. B, C, D)
- Time since injury ≤ 5 years vs >5 years

No adjustment to the significance level for testing will be made for subgroup analysis since all these subgroup analyses will be considered exploratory.

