8.5.2.2 Secondary Efficacy Endpoints

- For Change from baseline in GRASSP Bilateral PP total score to Study Day 169, analysis will be conducted using the same methodology as that used for the primary efficacy endpoint (sections 8.5.2.1 and 8.5.2.1.1).
- For Change from baseline in SCIM III Self Care score to Study Day 169, analysis will be conducted using the same methodology as that used for the primary efficacy endpoint (sections 8.5.2.1 and 8.5.2.1.1).
- Fisher's exact test at two-sided significance level 0.05 will be used to test if there is a difference of PGIC responses (1=`Much worse', 2=`Worse', 3=` A little worse', 4=`No change', 5=`A little better', 6=`Better, 7=`'Much better') at Study Day 169 between patients in treatment group and control group. In addition, Fisher's exact test to compare responder rate (proportion of patient in mITT Analysis set with responses of `A little better', `Better', or `Much better') at Study Day 169 between the two treatment groups will conducted. A descriptive table summarizing number and percentage of patients for each of the seven above responses by visit and treatment group will be created.

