8.5.2.3 Exploratory Efficacy Endpoints

For exploratory efficacy endpoints of changes from baseline in assessment results (as listed in section 3.1.2.5.1), analysis will be conducted using the same methodology as that used for the primary efficacy endpoint (sections $\underline{8.5.2.1}$ and $\underline{8.5.2.1.1}$).

For other exploratory efficacy endpoints at Study Day 169:

- ISNCSCI ASIA impairment scale (A, B, C, D, E) will be summarized descriptively as the number and percent of subjects with each response at each visit by treatment group.
- ISNCSCI Neurological Motor level will be summarized descriptively as the number and percent of subjects by body part by treatment group.
- ISNCSCI Neurological Sensory level will be summarized descriptively as the number and percent of subjects by body part by treatment group.
- ISNCSCI Neurological Level of Injury (NLI) will be summarized descriptively as the number and percent of subjects by body part by treatment group.
- ISAFSCI assessments: for each system/organ, shift table of baseline evaluation to Study Day 169 evaluation will be created.
- Clinical Global Impression of Change (CGIC) from GRASSP Prehension Performance Video Recordings. Assessments of Baseline compared to Day 169 will be completed and scores will be assigned using the 7-point Likert scale questions shown below and the Fisher's exact test at two-sided significance level 0.05 will be used to test if there is a difference in ratings (1= 'Much worse', 2='Worse', 3=' A little worse', 4='No change', 5='A little better', 6='Better, 7=''Much better') at Study Day 169 between patients in treatment group and control group. In addition, the Fisher's exact test will be used to compare responder rate (proportion of patient in mITT Analysis set with responses of 'A little better', 'Better', or 'Much better') at Study Day 169 between the two treatment groups. A descriptive table summarizing number and percentage of patients for each of the seven above responses by visit and treatment group will be created.

All efficacy endpoints will also be analyzed for Study Day 253 similar to the analysis conducted for Study Day 169 for each corresponding endpoint. All post treatment values up until Study Day 253 will be included in the analysis of treatment effect for Study Day 253.

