Therefore, ReNetX performed exploratory analyses on several endpoints in these subgroups, which suggested that three endpoints had visually a higher change from baseline in AXER-204 group compared to Placebo group, and proposed additional post hoc analyses that may reveal treatment effect for the following efficacy endpoints. Similar to the subgroup analyses (section 8.5.2.1.3), the alpha from the primary efficacy analysis has been used, so no adjustment to the significance level for testing will be made because all these analyses will be considered exploratory. For this reason, no formal conclusions can be drawn from any differences, and p-values will be provided for descriptive purposes only.

- **Primary efficacy endpoint:** Change from baseline in bilateral UEMS to Study Day 169 ranging from 0-50.
- **Secondary efficacy endpoint:** Change from baseline in GRASSP bilateral PP to Study Day 169 ranging from 0-40.
- Exploratory efficacy endpoint: Change from baseline in ISNCSCI bilateral motor score (including both upper and lower extremity for both left and right sides) to Study Day 169 ranging from 0-100.

• Including patients with AIS grade (B, C, D)

An analysis including patients with AIS grade (B, C, D) will be conducted in the mITT Analysis set. The same MMRM method as the primary analysis as described in section 8.5.2.1 will be used. Since subgroup analysis of AIS grade (A vs. B, C, D) on the primary efficacy endpoint have already been performed as part of the planned analysis, analysis will only be done on the secondary and exploratory efficacy endpoints.

• Including patients with no prior recent of study drug in Part 1

An analysis including patients with no prior receipt of study drug in Part 1 will be conducted in the mITT Analysis set. The same MMRM method as the primary analysis as described in section 8.5.2.1 will be used. Since subgroup analysis of prior receipt of study drug in Part 1 (yes vs. no) on the primary efficacy endpoint have already been performed as part of the planned analysis, analysis will only be done on the secondary and exploratory efficacy endpoints.

• Including patients with AIS grade (B, C, D) and no prior receipt of study drug in Part 1

An analysis including patients with AIS grade (B, C, D) and no prior receipt of study drug in Part 1 will be conducted in the mITT Analysis set. The same MMRM method as the primary analysis as described in section 8.5.2.1 will be used.

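### The three Day 169 secondary endpoints and the slope tests can each be called significant at two-sided 5%, with no link to UEMS, although the SAP reports that UEMS failed

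*Protocol*

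**What the plan says.** Protocol 15.7 sets one level for everything: "All inferential testing will be performed using two-sided 5% Type I error", and therefore "2-sided p-values $\leq 0.05$ will be considered statistically significant in this study". It calls UEMS change to Day 169 the first hypothesis test and then continues: "Additional secondary efficacy endpoints tested will be the change in GRASSP prehension performance from baseline to Study Day 169", adding SCIM self-care. It does not say what follows if the first test fails.

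The SAP makes UEMS the primary efficacy endpoint (2.1.2.2, 8.5.2.1). It adds PGIC responder rate as a third secondary endpoint (9.1) and numbers the secondaries 1st to 3rd (3.1.2.2 to 3.1.2.4), but never uses those numbers as a testing order. Table 6 in SAP 8.1 gives the rule for significance tests as "Two sided and use a 5% significance level". SAP 8.5.2.2 gives GRASSP and SCIM both the MMRM and the slope model. For PGIC it states: "Fisher's exact test at two-sided significance level 0.05 will be used to test if there is a difference of PGIC responses", and then adds a Fisher test of the responder rate.

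Multiplicity is mentioned twice. SAP 8.5.2.1.3 says: "No adjustment to the significance level for testing will be made for subgroup analysis since all these subgroup analyses will be considered exploratory". SAP 10.1, written after the Day 169 unblinding, reports that UEMS did not reach significance. Of the new post hoc analyses it says that "the alpha from the primary efficacy analysis has been used, so no adjustment to the significance level for testing will be made", that no formal conclusions follow, and that their p-values are descriptive.

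**The concern.** An order of tests controls error only if a failure stops the sequence or limits what follows. Neither document has such a rule. The secondaries are not marked as exploratory either: each has its own estimand, intercurrent-event strategy and sensitivity estimand. Slope is part of the secondary endpoints in Protocol 13.1.2.

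The gap matters because the primary result is known. SAP 10.1 reasons that the alpha has been used and so p-values can only describe, yet confines this to the post hoc analyses. The same reasoning covers the planned secondaries. As written, a secondary or slope result at p = 0.04 could be reported as statistically significant after the one test carrying the trial's alpha had failed.

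**Working it through.** **Inputs from the documents.** Level 0.05, two-sided, per test (Protocol 15.7; SAP Table 6). Three secondary endpoints at Day 169 (SAP 2.1.2.2, 8.5.2.2, 9.1). About 16 subjects per arm (Protocol 15.1).

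**Inputs assumed.** Correlation between test statistics, taken from 0 to 0.8, and the true PGIC responder rate, because the documents give neither.

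**The plan's own figure.** The plan states no family-wise error rate. Its one related calculation is the size for UEMS: difference 5, SD 4, 12 per arm for 80% power. The noncentral t gives 79.6% at 11 per arm and 83.3% at 12, so 12 is the smallest size reaching 80%. Only UEMS was sized.

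**Step 1, independent tests.** P(at least one false positive) = 1 − (1 − 0.05)³ = 1 − 0.8574 = 14.3%.

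**Step 2, Fisher's conservatism.** Enumerating all outcomes at 16 per arm, a nominal 5% Fisher test has a true size of about 1.8% to 2.0% for responder rates of 20% to 60%. At 2%: 1 − 0.95² × 0.98 = 1 − 0.8845 = 11.6%.

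**Step 3, correlated tests.** Let Z_j = √ρ·g + √(1−ρ)·e_j, with g and e_j independent standard normal, for UEMS and the three secondaries. A test rejects when |Z_j| exceeds 1.96 (2.33 for PGIC at 2%). Simulated under the global null:

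| ρ | Three at 5% | PGIC at 2% | Three at 5%, given UEMS failed | PGIC at 2%, given UEMS failed |
|---|---|---|---|---|
| 0 | 14.3% | 11.6% | 14.3% | 11.6% |
| 0.3 | 13.6% | 11.1% | 13.0% | 10.6% |
| 0.5 | 12.5% | 10.3% | 11.1% | 9.0% |
| 0.7 | 10.9% | 9.1% | 8.4% | 6.8% |
| 0.8 | 9.8% | 8.3% | 6.7% | 5.4% |

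**Step 4, check on subject-level data.** Two t-tests and an actual Fisher test, 16 per arm, responder rate 30%, at ρ = 0, 0.3, 0.5, 0.7, 0.8. Unconditional: 11.3%, 10.9%, 10.6%, 9.5%, 8.9%. Given UEMS failed: 11.3%, 10.5%, 9.4%, 7.4%, 6.2%. These lie close to the PGIC-at-2% columns, and higher at large ρ.

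**Step 5, slopes, indicative only.** Adding the GRASSP and SCIM slope tests to the PGIC-at-2% case, with an assumed correlation of 0.9 between slope and change, gives 15.4%, 14.8%, 13.8% and 12.4% at ρ = 0, 0.3, 0.5 and 0.7 (unconditional).

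**The case against.** The strongest reply is that this is not a confirmatory trial. Part 2 is Phase 2a with about 32 subjects, its primary objectives are safety, tolerability and pharmacokinetics, and all efficacy sits under secondary objectives. One contrast is named as the primary efficacy test, and the SAP openly reports that it failed. This stands as an argument about severity: strict family-wise control is not obligatory here. It does not cover the wording, because the Protocol states formal hypotheses, sizes the trial on UEMS and attaches the term statistically significant to any p-value at or below 0.05.

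A reader might also count the Day 253 repeats in the family, because SAP 8.5.2.3 says: "All efficacy endpoints will also be analyzed for Study Day 253 similar to the analysis conducted for Study Day 169 for each corresponding endpoint". The documents do not support that. The sentence stands in an exploratory section, as does its counterpart in SAP 3.1.2.5.2. Protocol 15.10.1 lists change to each post-baseline visit for UEMS, GRASSP and SCIM as exploratory, and every secondary estimand stops at Day 169. Likewise, the seven-category PGIC test is an extra analysis and not the defined endpoint, so it is not counted above.

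Finally, the magnitude depends on correlations that nobody has stated. That is correct, and is why only ranges are given.

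**Conclusion.** The point holds for the three Day 169 secondary endpoints and the GRASSP and SCIM slope tests. Nothing in the plan stops any of them being called statistically significant after UEMS has failed, and SAP 10.1 applies its own reasoning about spent alpha only to the post hoc analyses.

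For the three secondaries the false-positive chance under the global null is about 8% to 14%, against 5% for a single test. Given that UEMS failed, it is about 5% to 14%. Both ranges assume equal correlations of 0 to 0.8 and allow PGIC a true size of either 5% or about 2%. A reader might take the unconditional range as the risk after the failed primary. With positive correlation the conditional risk is lower, and at 0.8 it comes close to 5%.

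A reader might also infer that an unsupported claim has already been made. The documents show only that the wording would permit one. Severity is low to moderate.

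**What to change.** Add a dated item to SAP section 10, marked as made after the Day 169 unblinding:

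- Because UEMS at Day 169 was not significant, p-values for GRASSP prehension performance, SCIM III self-care, PGIC (responder and seven-category) and all slope analyses are descriptive and support no formal conclusion, as 10.1 already says of the post hoc analyses.
- Report these results as estimates with 95% confidence intervals.
- The significance sentence in Protocol 15.7 and the level in SAP Table 6 apply, for claims of efficacy, only to the UEMS Day 169 MMRM test.

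Do not write a fixed testing sequence into SAP 8.5.2. Placed there now it would look prespecified, and it would stop at its first step anyway.

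The cost is wording. The MMRM already yields intervals; an interval for the PGIC responder difference, which 8.5.2.2 does not mention, is a minor addition. The real price is that a secondary result with p at or below 0.05 can no longer be called statistically significant. Since the change only removes possible claims, its late date cannot favour the drug.

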## 15.8. Subject Disposition and Exposure

The numbers of subjects randomized (Part 2 only), completing or withdrawing, along with reasons for withdrawal, will be summarized by dose (Part 1) and treatment group (Part 2). Tabulation of the number of doses of investigational product, duration of treatment as well as total dose given will be provided.

## **15.9.** Demographics and Baseline Characteristics Analyses

Demographic variables (age, sex, race, and ethnicity) as well as height (cm), weight (kg), Body Mass Index (BMI), temperature, heart rate, blood pressure and respiratory rate or pulse oximetry (from the vital signs) at baseline will be summarized using descriptive statistics. All demographic data will be provided in a data listing.

## 15.10. Efficacy Endpoints

For Part 1 efficacy, outcomes will be presented by each dosing cohort, with no inferential assessments among cohorts planned. Thus, for Part 1, efficacy will be presented only descriptively.

For Part 2, changes from pre-treatment to each on-treatment time point will be calculated, with the primary time point at Day 169. Shifts over time in ordinal endpoints will be presented, with comparisons between treatment groups assessed using a CMH row mean scores statistic at each time point. Slope of change will also be evaluated. Part 2 efficacy analysis is described in the following sections.

### 15.10.1. Part 2 Efficacy Endpoints

Change in bilateral UEMS from baseline to Day 169 will be evaluated as a key secondary endpoint for the trial.

Baseline bilateral UEMS is defined as the last non-missing bilateral UEMS prior to first treatment in Part 2.

The null and alternative hypothesis for this study are as follows:

 $H_0: \mu_A = \mu_P$ 

 $H_A: \mu_A \neq \mu_P$ 

ReNetX Bio, Inc.

Where  $H_0$  and  $H_A$  refer to the Null and alternative hypothesis to be tested in this study,  $\mu_A$  and  $\mu_P$  refers to the mean change in bilateral UEMS from baseline to Study Day 169 for subjects randomized to AXER-204 and Placebo groups respectively.

Analysis to compare the change in bilateral UEMS from baseline to each post baseline visit will be based upon a mixed-effects model for repeated measures (MMRM) for the double-blind period using the FAS population.

Additional secondary efficacy endpoints will include change from baseline to Day 169 in the total GRASSP prehension performance score and change from baseline to Day 169 in SCIM III self-care score. The analyses for these scores will be handled the same way as the key secondary endpoint.

Exploratory efficacy endpoints will include changes from baseline to each post baseline value in each of the following endpoints.

- Change from baseline to each post baseline value for bilateral UEMS, GRASSP prehension performance, and SCIM III self-care scores.
- Bilateral ISNCSCI sensory and lower extremity motor scores
- Bilateral GRASSP strength, sensation and prehension ability scores
- Patient Reported Outcomes
  - CUE-Questionnaire (CUE-Q)
  - PGIC Chronic SCI
  - SF-36 v2 Health Survey
  - Neuro-QOL Item Bank v1.0 Upper Extremity Function (Fine Motor, ADL)
- ISAFSCI. The ISAFSCI will be used to document autonomic control of the heart, blood pressure, sweating and temperature regulation. Lower urinary tract function, bowel function, and sexual function will be scored.

Responder analyses may be performed to compare the proportion of responders in each treatment group. Details of responder analyses with thresholds used to define clinically meaningful improvements will be defined in the SAP.

Sensitivity analyses of the secondary and exploratory endpoints may be performed if the outcomes warrant further analysis.

## 15.11. Safety Endpoints

The safety analysis will be descriptive in nature. All safety data will be listed, and data will be tabulated by dose (Part 1) and treatment group (Part 2) where the data warrant. Safety data include:

- AEs, including assessment of lumbar infusion site
  - Events occurring prior to the first dose of investigational product or placebo will be defined as pre-treatment events.

- For Part 1, TEAEs will be defined as any AE occurring during or after the injection of study drug. This will therefore include all events occurring through Day 29/ET.
- For Part 2, TEAEs will be limited to those events occurring within 28 days after the last visit.

Incidence of AEs will be summarized for each treatment group/cohort by MedDRA system organ class (SOC) and preferred term, sorted in descending frequency by SOC, and then by preferred term within SOC. These summaries will be given by treatment in separate tables for each of the following TEAE event sets:

- All events
- Treatment related events (defined by a relationship to study drug of possible, probable, or definite).
- Serious adverse events
- Events leading to premature discontinuation from study
- Events by maximum severity
- AEs of Special Interest, ie, events relating to the lumbar puncture procedure (eg, infection, headache, back pain, excessive CSF leakage requiring blood patch).

Other safety outcomes will include:

- Clinical laboratory tests, including hematology, chemistry, metabolic, and urinalysis. Changes over time will be presented. Potentially clinically significant (PCS) ranges will be defined and used to determine the incidence of subjects experiencing newonset PCS laboratory values, where new-onset is defined as a PCS value for a subject following initiation of study treatment for which the subject did NOT have a PCS value for that analyte PRIOR to initiation of study treatment.
- Vital signs including: respiratory rate or pulse oximetry, heart rate, temperature, and blood pressure, as per the schedule of events. BMI will be assessed, with height collected only at screening.
- Physical examination
- 12-lead ECG. ECG parameters will be analyzed in a fashion similar to that of clinical laboratory parameters.

Condition-specific safety outcomes will include:

- ISNCSCI, GRASSP and all of the neurological measures evaluated for efficacy
- Spasticity (Modified Ashworth Scale). A clinician administered examination for spasticity which measures muscle tone. A score of 0-4 is assigned to each muscle group evaluated. Note: Testing will exclude fingers and thumb.
- Pain (BPI). A self-administered questionnaire used to assess the severity of a subject's pain and the impact of this pain on the subject's daily functioning.

Concomitant treatments will be assessed according to the timing of their start/stop dates as they relate to the study drug treatment, as follows:

- Prior. Medications with start AND stop date before date of first dose of study drug or placebo.
- Concomitant. Medications with subject exposure that includes at least one dose of study drug or placebo.
- New-onset medications. Concomitant medications with a start date AFTER the first dose of study drug or placebo. New-onset medications are a subset of the full set of concomitant medications.
- Post-treatment medications. Medications with a start date at least 28 days AFTER the last dose of study drug or placebo.

Changes from pre-treatment will be calculated in a similar fashion as for the efficacy endpoints, but no inferential statistics will be provided for safety endpoints. Shifts from baseline in ECG will be tabulated for heart rate and QTcF. Other endpoints will be assessed according to the scale of the variable.

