### 14.2.3. Adverse Events of Special Interest (AESI)

Adverse Events of Special Interest (AESI) for this study include possible allergic/immune reactions to administration of a protein therapeutic, AEs generally associated with lumbar puncture, and theoretical AEs arising from axon growth. No AESI have been identified from non-clinical toxicology studies with AXER-204. The following are considered AEs of Special Interest for this study:

- Immune/Allergic reactions: fever, rash, arthralgia, myalgia, hematuria, proteinuria, serositis, central nervous system complications, and hemolytic anemia. Injection site reactions may occur
- Events relating to the lumbar puncture procedure: infection, postdural puncture headache, bleeding, brainstem herniation, meningitis, back pain, excessive CSF leakage requiring blood patch
- Complicating infections: discitis and vertebral osteomyelitis
- Neurological symptoms or injuries: low back pain, radicular injury, abducens palsy
- Other: late onset of epidermoid tumors of the thecal sac, increased pain, increased spasticity

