The number and percentage of subjects reporting each TEAE will be summarized by SOC and PT, or PT. Tables will be sorted in descending overall frequency by SOC, and then in descending overall frequency by PT within SOC, and then alphabetically. The following summaries will be produced:

- TEAEs, by SOC and PT;
- TEAEs, by PT;
- TEAEs, by SOC and PT and maximum severity;
- Treatment-related TEAEs, by SOC and PT;
- Lumbar Puncture procedure related TEAEs, by SOC and PT (Part 2 only);
- TEAEs leading to discontinuation from study, by SOC and PT;
- TEAEs of Special Interest, by SOC and PT;
- Serious TEAEs, by SOC and PT;
- Treatment-related serious TEAEs, by SOC and PT;
- Lumbar Puncture procedure related serious TEAEs, by SOC and PT (Part 2 only);
- Serious TEAEs leading to discontinuation from study, by SOC and PT;
- Serious TEAEs leading to death, by SOC and PT.

In the above summaries, subjects with more than one AE within a particular SOC are counted only once for that SOC. Similarly, subjects with more than one AE within a particular PT are counted only once for that PT. For summaries by maximum severity, subjects with multiple AEs within a particular SOC or PT will be counted under the category of their most severe AE within that SOC or PT.

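### Protocol 15.11 defines the table of adverse events of special interest (AESI) as lumbar-puncture events only, contradicting the protocol's own list in 14.2.3, and the SAP uses the term without saying which definition applies

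*Protocol*

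**What the plan says.** Protocol 14.2.3 opens by saying that the AESI for the study "include possible allergic/immune reactions to administration of a protein therapeutic, AEs generally associated with lumbar puncture, and theoretical AEs arising from axon growth". It then gives five bullets:

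- "Immune/Allergic reactions: fever, rash, arthralgia, myalgia, hematuria, proteinuria, serositis, central nervous system complications, and hemolytic anemia", with injection-site reactions added at the end;
- "Events relating to the lumbar puncture procedure: infection, postdural puncture headache, bleeding, brainstem herniation, meningitis, back pain", plus CSF leakage needing a blood patch;
- "Complicating infections: discitis and vertebral osteomyelitis";
- "Neurological symptoms or injuries: low back pain, radicular injury, abducens palsy";
- an 'other' bullet with late epidermoid tumors of the thecal sac, increased pain and increased spasticity.

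Protocol 14.2.5.5 requires AESI to reach the sponsor within 24 hours and to be assessed by the Medical Monitor.

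Protocol 15.11 lists the event sets to be tabulated. The last is "AEs of Special Interest, ie, events relating to the lumbar puncture procedure", followed by a bracket of examples, all of them lumbar-puncture events.

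SAP 8.8.2 plans an AESI listing, a row in the overview table, and a table of "TEAEs of Special Interest, by SOC and PT". It separately plans tables of events related to the lumbar-puncture procedure, for Part 2 only. Neither 8.8.2 nor any other section of the SAP defines AESI or refers to 14.2.3 or 15.11 for a definition.

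**The concern.** The same label has two meanings in one protocol. For expedited reporting it covers five groups. For the summary table, 15.11 introduces its description with 'ie', which restates the whole set, and gives only lumbar-puncture events.

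The difference falls on the drug-specific risks. Safety and tolerability against placebo is a primary objective of Part 2 (Protocol 6.2.1), in the first evaluation of this protein in humans (5.3). Placebo subjects receive intrathecal injections at the same intervals and volume (Synopsis, Reference therapy), so lumbar-puncture events are to be expected in both arms. The lead sentence of 14.2.3 ties the other AESI to giving a protein and to axon growth, and those are the groups that a lumbar-puncture definition omits. The terms in the immune/allergic bullet also span several organ systems. With about 16 subjects per arm, a pattern among them could be split into single counts across the rows of a general table by system organ class, and an AESI table is where a reader would look for it.

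**Working it through.** No power, alpha or event-rate figure enters this point, so the check is a side-by-side comparison with a hand count.

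**Step 1. Compare 14.2.3 with 15.11.** The strict reading of 15.11 admits only the bullet that 14.2.3 itself labels as lumbar-puncture events. The wide reading also treats complicating infections and neurological injuries as lumbar-puncture complications. That is plausible, because 15.11's own examples of lumbar-puncture events include infection and back pain.

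| Group in 14.2.3 | Named terms | Strict reading | Wide reading |
|---|---|---|---|
| Immune/allergic (with injection-site reactions) | 10 | out | out |
| Lumbar puncture | 7 | in | in |
| Complicating infections | 2 | out | in |
| Neurological symptoms or injuries | 3 | out | in |
| Other (late epidermoid tumors, increased pain, increased spasticity) | 3 | out | out |
| Total | 25 | | |

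- Strict: 4 of 5 groups are out, with 10 + 2 + 3 + 3 = 18 of 25 named terms.
- Wide: 2 of 5 groups are out, with 10 + 3 = 13 of 25 named terms.

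Back pain sits inside the lumbar-puncture set, so the pain item left out on either reading is increased pain.

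**Step 2. See whether the SAP settles it.** SAP 8.8.2 places no lumbar-puncture limit on its three AESI outputs. It also gives no definition, no cross-reference and no rule for identifying the events. SAP section 9, which records changes from the protocol's analyses, does not mention AESI.

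**Step 3. See where the omitted events would still appear.**

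- Every treatment-emergent event is tabulated by arm, system organ class and preferred term, with further tables for related events, serious events and maximum severity, and all safety data are listed (Protocol 15.11; SAP 8.8.2).
- Blood and protein in urine are among the urinalysis tests (SAP 8.8.3).
- Anti-drug antibody status is summarised (SAP 8.7).
- Brief Pain Inventory scores and bilateral Modified Ashworth scores are compared between arms with the same models as the primary efficacy endpoint (SAP 8.8.7).

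The literal effect of 15.11 is therefore confined to the outputs that carry the AESI label.

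**The case against.** The best answer is that the full list already governs. Section 14.2.3 is the protocol's AESI section. Sites must report AESI within 24 hours under 14.2.5.5, so the events are identified against that list. Protocol 15.3 leaves further analysis detail to the SAP, and the SAP drops the lumbar-puncture limit. The SAP also gives procedure-related events tables of their own, which suggests that its author did not equate the two sets. The eCRF that the SAP cites may hold an AESI flag that cannot be seen here.

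Most of this stands. It makes the full list the likelier reading of the SAP. It does not secure that reading, because the SAP never states it and 15.11 still says otherwise.

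Several stronger inferences are tempting, and the documents do not support them:

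- **That immune, pain or spasticity events would go unreported.** They remain in the outputs given in step 3 of the working.
- **That the SAP's AESI table will hold lumbar-puncture events only.** The SAP does not carry the restriction. Section 9's silence proves nothing either way, because that section is not exhaustive. The treatment-emergent window, for example, moves from 28 days after the last visit (Protocol 15.11, Part 2) to 28 days after the last injection (SAP 8.8.2) without being listed there.
- **That the AESI and lumbar-puncture tables would duplicate each other.** Protocol 14.2.5.2 has the investigator judge relatedness to the procedure for every event, so the lumbar-puncture tables appear to rest on causality and not on event type.
- **That four of five groups is a firm figure.** It is the upper end of a range that depends on how two bullets are read.

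**Conclusion.** The contradiction between Protocol 15.11 and 14.2.3 is real, and the SAP leaves it open. Taken at its word, 15.11 yields an AESI table without the immune/allergic and 'other' groups. That is two of the five groups at least and four at most, or 13 to 18 of 25 named terms. The range rests on reading 'ie' as a definition and on the hand count above.

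This is an inconsistency in safety reporting and a minor one. It bears on a primary objective, because the groups at issue are those most specific to the drug, but it touches only the AESI outputs. It has no bearing on sample size, power or alpha.

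**What to change.** - **Protocol 15.11:** replace the lumbar-puncture wording with a reference to adverse events of special interest as listed in Section 14.2.3.
- **SAP 8.8.2:** define AESI by that same list, and apply it to the listing, the overview row and the table by system organ class and preferred term. One line on how the events are identified (an eCRF flag or a preferred-term list) would make this reproducible.
- **Optional:** tabulate by AESI group as well, so that related terms from different organ systems appear together.

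The cost is wording in two documents and minor programming, with no new data. SAP section 10 records that some sponsor staff had seen unblinded Day 169 results before the final database lock. That favours adopting the 14.2.3 list as it stands, since it is already in the protocol and leaves no choice of definition to anyone who has seen results.
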